AR101 consists of peanut flour characterized for quantities of specific peanut allergens and is formulated with bulking and flow agents in graduated doses. AR101 will be provided in pull-apart capsules containing 0.5, 1, 10, 20, or 100 mg peanut protein. AR101 will also be provided as 300 mg peanut protein in foil-laminate sachets. Capsules/sachets will be opened; the contents delivered over an age-appropriate, semisolid, vehicle food; and mixed thoroughly.

The sponsor will supply the AR101 for this study. Trained study site personnel will dispense AR101 to the parent/caregiver as appropriate for the assigned dose level.

Reference Therapy, Dose, and Mode of Administration:

Placebo is formulated with the same inactive ingredients as AR101 and without peanut flour. Placebo containing excipients that are color-matched with the peanut flour will be provided as matching capsules identical to the AR101 capsules. Matching placebo-containing sachets are also provided. Capsules/sachets will be opened; the contents delivered over an age-appropriate, semisolid vehicle food; and mixed thoroughly.

The sponsor will supply the placebo for this study. Trained study site personnel will dispense placebo to the parent/caregiver as appropriate for the assigned dose level.

Duration of Treatment:

The total duration of treatment is approximately 12 months (eg, 48-54 weeks) for each subject.

The end of the study is defined as the last assessment for the last subject in the study.

Statistical Methods:

The statistical methods and data presentations for reporting the study will be described in detail in the statistical analysis plan. No interim analyses are planned.

All efficacy analyses will be conducted using the intent-to-treat (ITT) population, defined as all subjects randomly assigned to study treatment who receive any part of 1 dose of study product. Randomization will be central and treatment allocation will be 2:1 (AR101 or placebo). Randomization will be stratified by geographic region (North America, Europe); at least 30% of subjects are planned to be enrolled in Europe.

The primary and secondary efficacy endpoints are defined by major health authority region (North America and Europe):

Primary Efficacy Endpoint:

- **North America:** The primary efficacy endpoint is the proportion of subjects treated with AR101 compared with placebo who tolerate an at least 600 mg single dose of peanut protein with no more than mild allergy symptoms during the exit DBPCFC.

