 - The Farrington-Manning test will be used to test the null hypothesis that the difference in desensitization response rate (AR101-placebo) is equal to 0.15 at the two-sided 0.05 significance level. Desensitization response rates and associated 95% CIs will be presented for each treatment group using exact Clopper-Pearson CIs.
- **Europe:** The primary efficacy endpoint is the proportion of subjects treated with AR101 compared with placebo who tolerate an at least 1000 mg single dose of peanut protein with no more than mild allergy symptoms during the exit DBPCFC.
 - The Farrington-Manning test will be used to test the null hypothesis that the difference in desensitization response rate is 0 at the two-sided 0.05 significance level. Desensitization response

rates and associated 95% CIs will be presented for each treatment group using exact Clopper-Pearson CIs.

Secondary Efficacy Endpoints: The following secondary efficacy endpoints will be evaluated in hierarchical order by region (North America and Europe) if the primary efficacy endpoint analysis is significant at the 0.05 level.

North America

1. Proportion of subjects who tolerate an at least 300 mg single dose of peanut protein with no more than mild allergy symptoms during the exit DBPCFC.
2. Proportion of subjects who tolerate an at least 1000 mg single dose of peanut protein with no more than mild allergy symptoms during the exit DBPCFC.
3. The maximum severity of allergy symptoms after consuming peanut protein during the exit DBPCFC.

Europe

1. Proportion of subjects who tolerate an at least 600 mg single dose of peanut protein with no more than mild allergy symptoms during the exit DBPCFC.
2. Proportion of subjects who tolerate an at least 300 mg single dose of peanut protein with no more than mild allergy symptoms during the exit DBPCFC.
3. The maximum severity of allergy symptoms after consuming peanut protein during the exit DBPCFC.

Safety Endpoints:

All safety analyses will be performed using the safety population, defined as all subjects who receive any randomized study treatment. Safety data will be summarized and listed by treatment received.

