5.2.3.1 Initial Dose-Escalation Procedures

Initial dose-escalation procedures are listed in [Appendix 5](#). Subjects may have clear liquids or flavored gelatin during the dosing procedures.

Day 1

Subjects will be required to discontinue antihistamines and other medications that could interfere with the assessment of an allergic reaction for 5 half-lives of the medication before the first day of dose escalation.

Study product will be administered in 4 increasing doses in a stepwise manner in 20- to 30-minute intervals as tolerated. The 4 doses and cumulative dose of study product to be consumed on day 1 are shown in [Table 1](#).

Table 1: Study Product Single Doses and Cumulative Dose on Day 1

Dose Number	Study Product Dose (mg)	Cumulative Dose (mg)
1	0.5	0.5
2	1	1.5
3	1.5	3
4	3	6

The time points for study product dosing and assessments of vital signs and allergic reaction are provided in [Table 2](#). Subjects who develop dose-limiting, moderate, or severe allergy symptoms at any dose of study product, or use rescue medications (except ≤ 2 doses of antihistamines, [Section 8.6.3.1](#)) will stop dose escalation and discontinue early from the study ([Section 5.3](#)).

Table 2: Initial Dose-Escalation Day 1 Procedures

Study Product Dose (Timing) Time Point	Administer Study Product	Vital Signs [1]	Assess Allergy Symptoms
Predose		X	
0.5 mg	X		
15-30 min postdose		X	X
1 mg (20-30 min after previous dose) [2]	X		
15-30 min postdose		X	X
1.5 mg (20-30 min after previous dose) [2]	X		
15-30 min postdose		X	X
3 mg (20-30 min after previous dose) [2]	X		
15-30 min postdose		X	X
Approximately every 30 min until at least 90 min after last dose or end of observation per allergy symptoms [3]		X	X

[1] Vital signs include blood pressure, heart rate, temperature, respiratory rate, and oxygen saturation level.

[2] If the previous dose was tolerated ([Section 8.6.1.2](#)). If the subject has dose-limiting, moderate, or severe symptoms at any dose, or requires rescue medications (except ≤ 2 doses of antihistamines, [Section 8.6.3.1](#)), stop dose escalation and discontinue the subject early from the study. If 3 mg is tolerated, the subject will return for a single 1 mg dose on day 2.

[3] The length of observation is based on signs/symptoms of allergic reaction per [Section 8.6.1](#).
Min, minutes.

Day 2

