5.3 Early Discontinuation

Early treatment discontinuation is defined as *permanent* cessation of study product administration anytime before completing the exit DBPCFC. Subjects who discontinue early will have early discontinuation procedures approximately 14 days after their last dose of study product according to the schedule of activities ([Appendix 5](#)).

Subjects with unresolved adverse events at early discontinuation or who had GI adverse events of interest ([Section 8.6.6.2.1](#)) will have safety follow-up per [Section 5.5](#).

Temporary treatment interruption (eg, due to an adverse event) will not be considered early discontinuation.

The primary reasons for early discontinuation of study product are listed in [Table 4](#).

Table 4: Primary Reasons for Early Discontinuation

Category Reason	Comment on Criteria
Protocol/ Investigator-Initiated	

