10.2 Analysis Populations

The ITT population (ie, full analysis set) will be defined as all subjects who receive any part of 1 dose of study product. The ITT population will be used for all efficacy analyses unless otherwise specified, and analyzed according to randomized treatment. If no subjects receive the incorrect treatment, the ITT population will be the same as the safety population.

The completer population will be defined as all subjects in the ITT population who complete study treatment and have an evaluable exit DBPCFC (completion of at least the peanut food challenge day).

The per protocol population may be defined if it is sufficiently different from the completer population. The per protocol population will include all subjects in the completer population who have no major protocol deviations that may influence the desensitization response.

The safety population will be defined as all subjects who receive any randomized study treatment (ie, who receive any part of 1 dose of study product and complete 1 study visit). The safety population will be used for all safety analyses and analyzed according to treatment received.

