10.5 Analysis of Efficacy

10.5.1 Primary Efficacy Analyses

The primary objective assesses the efficacy of AR101 treatment in peanut-allergic subjects aged 1 to < 4 years.

The primary efficacy endpoints are defined by major health authority region.

- **North America:** The primary efficacy endpoint is the proportion of subjects treated with AR101 compared with placebo who tolerate an at least 600 mg single dose of peanut protein with no more than mild allergy symptoms during the exit DBPCFC.
- **Europe:** The primary efficacy endpoint is the proportion of subjects treated with AR101 compared with placebo who tolerate an at least 1000 mg single dose of peanut protein with no more than mild allergy symptoms during the exit DBPCFC.

The ITT population and Farrington-Manning test will be used for these analyses. Subjects tolerating a single dose of at least 600 mg peanut protein for North America and at least 1000 mg peanut protein for Europe will be considered responders; subjects who do not tolerate a single dose of at least 600 mg peanut protein for North America and at least 1000 mg peanut protein for Europe will be considered nonresponders. Nonresponders will also include subjects who withdraw consent or discontinue early anytime before the exit DBPCFC.

Desensitization response rates and associated 95% CIs will be presented for each treatment group using exact Clopper-Pearson CIs. The 95% CI for the treatment difference (desensitization rate for AR101 treatment minus desensitization rate for placebo) will be based on the Farrington-Manning method. The primary efficacy endpoint for North America will be considered met if the lower bound of the 95% CI is greater than the prespecified margin of 0.15. The primary efficacy endpoint for Europe will be considered met if the lower bound of the 95% CI is greater than 0.

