10.6 Analysis of Safety

All safety analyses will be performed using the safety population. Safety data will be summarized and listed by treatment received.

Safety data will be collected from signed informed consent and assent (where required) through 14 days after the last dose of study product, or through study exit for subjects receiving AR101 treatment in a follow-on study. Safety follow-up data will be collected for at least 30 days after early discontinuation or study exit for subjects with unresolved adverse events, or for at least 6 months after early discontinuation or study exit for subjects with GI adverse events of interest.

Adverse events will be classified by system organ class and coded to preferred term using MedDRA. Adverse events will be classified by severity using the CoFAR grading system for allergic reactions, modified EAACI guidelines for anaphylaxis, and CTCAE for all other adverse events ([Section 8.5](#)).

Summaries of the safety of AR101 and placebo treatment during the study will include the following:

- Overall summary of adverse events
- Incidence of all nonserious and serious adverse events
- Incidence of adverse events by severity grade
- Incidence of adverse events during up-dosing and maintenance
- Incidence and severity of treatment-related adverse events
- Incidence of treatment-related adverse events during up-dosing and maintenance
- Incidence of dose modifications
- Exposure-adjusted event rates for the most frequent adverse events (ie, adverse events in $\geq 5\%$ of the safety population)
- Exposure-adjusted event rates for the most frequent treatment-related adverse events (ie, adverse events in $\geq 5\%$ of the safety population)

- Incidence of early treatment discontinuation due to adverse events and due to chronic or recurrent GI adverse events
- Separate summaries will be presented for anaphylaxis, allergic reaction adverse events, use of epinephrine, and accidental/nonaccidental food allergen exposure

Adverse events with onset before the first dose of study treatment will be listed only.

All medications will be coded using the World Health Organization Drug Dictionary (WHO-DD). Medications will be listed and summarized by Anatomical Therapeutic Chemical (ATC) classification system level 1 and preferred name.

- Prior and concomitant medications, excluding rescue medications, will be summarized separately by ATC class, preferred name, and treatment.

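### Does the visit condition in the Section 10.2 safety population leave dosed children out of the safety tables?

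*Combined protocol and SAP*

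**What the plan says.** Section 10.2 opens its definition of the safety population with everyone who receives randomized treatment. A parenthesis introduced by ie then restates this as subjects "who receive any part of 1 dose of study product and complete 1 study visit". The synopsis, under Safety Endpoints, gives only the unrestricted form: "defined as all subjects who receive any randomized study treatment".

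The synopsis describes the ITT population as "defined as all subjects randomly assigned to study treatment who receive any part of 1 dose of study product". Section 10.2 likewise asks only for part of a dose, with no visit condition. The same section links the two sets: "If no subjects receive the incorrect treatment, the ITT population will be the same as the safety population".

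Section 10.6 makes the definition matter: "All safety analyses will be performed using the safety population".

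**The concern.** A restatement should not add a condition, and this one does. Neither the main clause, the synopsis nor the ITT definition mentions a visit. The protocol does not say which visit counts or what completes it; Appendix 3 says only that a study site visit is one held on site.

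Suppose the words mean a finished treatment visit. A child with dose-limiting, moderate or severe symptoms on day 1 "will stop dose escalation and discontinue early from the study". If the parent took such a child away before the visit ended and never came back, the child would have been dosed but would have no finished treatment visit. The primary analysis would still count the child, because "Nonresponders will also include subjects who withdraw consent or discontinue early anytime before the exit DBPCFC". The adverse event, anaphylaxis and epinephrine summaries would not. That would be an exclusion made after dosing and related to the outcome, which a safety population exists to prevent.

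**Working it through.** The check is mainly a comparison of definitions. Let D be the children who receive any part of a dose, and V those who complete one study visit.

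| Place | Set defined |
|---|---|
| Synopsis, ITT | D |
| Section 10.2, ITT | D |
| Synopsis, safety | D |
| Section 10.2, safety, main clause | D |
| Section 10.2, safety, parenthesis | D and V |
| Section 10.2, link sentence | safety = ITT = D, unless someone receives the wrong treatment |

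All the entries agree if and only if every child in D is also in V. The question is whether that holds.

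1. Section 4.1 (criterion 4) requires a reaction in the screening food challenge. Section 9.2 spreads that challenge over two days. Section 5.1.3 requires all screening results before eligibility is decided, and Section 5.2.2 places randomization after that.
2. Appendix 3, Section 2.4, does not allow food challenges to be done remotely, so these screening days are on site even under pandemic rules.
3. Section 3.1 has the first dose given under supervision at the site on day 1.
4. Section 5 counts screening as one of the study periods.

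On the plain words, then, every child in D has completed at least one visit before the first dose. D and V is the same as D, and all six entries agree.

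On the strict reading (a finished visit at or after first dosing), a child is lost only if both of these hold:

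- The day 1 visit is not completed. Stopping for symptoms is a specified course of that visit. So is prolonged observation after a severe reaction, at the site or an emergency facility (Section 8.6.1). Neither makes the visit incomplete.
- The child has no later visit. Section 5.3 provides one: "Subjects who discontinue early will have early discontinuation procedures approximately 14 days after their last dose of study product".

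The documents give no count of such children. To bound the effect, take the planned arms of 88 and 44 (Section 10.3). If k of n children have an event and one of the k is removed, the rate falls by

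k/n − (k − 1)/(n − 1) = (1 − p)/(n − 1), with p = k/n.

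For n = 88:

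- k = 1: 1/88 to 0/87, a fall of 1.14 points
- k = 2: 2/88 (2.27%) to 1/87 (1.15%), a fall of 1.12 points
- k = 44: 44/88 (50.0%) to 43/87 (49.4%), a fall of 0.57 points
- k = 80: 80/88 (90.9%) to 79/87 (90.8%), a fall of 0.10 points

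The largest shift from one child is 1/88 = 1.14 points in the AR101 arm and 1/44 = 2.27 points in the placebo arm. If two AR101 children were lost and they were the only two with the event, the shift would be 2/88 = 2.27 points.

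**The case for a change.** The best case for a change is that a core population definition should not rest on inference. Section 5.2.3 uses the term study visit in its heading for treatment-period procedures, so a strict reader has some footing. The early discontinuation visit does not protect every child, since Section 5.6 provides for loss to follow-up. For a rare event the effect is large in relative terms: going from 2 of 88 to 1 of 87 roughly halves the rate. Deleting a few words would cost almost nothing.

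The observation about the text stands: the parenthesis is loose and the visit is undefined. The consequence does not.

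- The strict reading has to supply a word the sentence lacks. It also has to overrule the unrestricted main clause, the synopsis and the sentence equating the two populations. That sentence recognises only one source of difference, receipt of the wrong treatment.
- The halved rate requires the one child who leaves on day 1 and never returns to be one of only two severe cases. Section 8.6.1 keeps a child with severe symptoms under observation for at least 3 hours after they resolve.
- Whole-study event rates from ARC003 cannot size the effect, because only events at the first dosing visit are exposed to it. Section 1.2.2 says most epinephrine use in ARC003 followed dosing at home during up-dosing and maintenance. Those children had already been through treatment visits.

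Section 1.2.2 also reports the same numbers in the ARC003 ITT and safety populations at ages 4 to 17, 372 and 124. The ARC003 definitions are not given, so this is only suggestive.

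**Conclusion.** The visit condition is redundant wording and is not shown to exclude anyone. Read with the rest of Section 10.2 and the synopsis, the safety population is every child who receives any study product, grouped by treatment received. An analyst would program it that way.

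This rests on screening visits counting as study visits, or failing that, on an attended day 1 visit counting as completed even when dosing stops early. If both failed, the effect would be at most 1.14 points on an AR101 rate, or 2.27 on a placebo rate, for each single child lost. The number of such children is unknown and may well be zero. The Section 10.6 analyses are descriptive summaries, so no test would change. Event collection and 24-hour reporting (Sections 8.7.1 and 8.7.2) do not depend on this definition, and the efficacy endpoints use the ITT population.

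Removing the words at a later revision would be a tidy edit. No result or conclusion is shown to depend on it, so no change to the plan is called for. The protocol leaves further detail to a statistical analysis plan, and the supplied text contains nothing from it on this point.

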10.3 Determination of Sample Size

A sample size of 132 subjects randomly assigned at a ratio of 2:1 to AR101 (88 subjects) or placebo (44 subjects) provides sufficient power to detect a treatment difference for the primary efficacy analysis for each major health authority region (North America and Europe) ([Section 10.5.1](#)).

For North America, the sample size provides 85% power to demonstrate a significantly higher desensitization response rate with AR101 compared with placebo with an at least 15% margin for the primary efficacy endpoint of the proportion of subjects tolerating an at least 600 mg single dose of peanut protein with no more than mild allergy symptoms during the exit DBPCFC. The sample size calculations are based on the Farrington and Manning method ([Farrington, 1990](#)) for the difference in proportions and assume a type I error of 0.05, 2-sided test, a desensitization rate based on the DBPCFC of 55% in AR101-treated subjects, and a maximum desensitization rate of 15% in placebo-treated subjects, conducted in the ITT population.

For Europe, the sample size provides > 95% power to demonstrate a significantly higher desensitization response rate with AR101 compared with placebo for the primary efficacy endpoint of the proportion of subjects tolerating an at least 1000 mg single dose of peanut protein with no more than mild allergy symptoms during the exit DBPCFC. The sample size calculations are based on the Farrington and Manning method for the difference in proportions and assume a type I error of 0.05, 2-sided test, a desensitization rate based on the

DBPCFC of 50% in AR101-treated subjects, and a maximum desensitization rate of 10% in placebo-treated subjects, conducted in the ITT population.

The desensitization rates used in the sample size calculations account for an estimated 25% of subjects across both treatment groups to drop out or discontinue early from the study; these subjects will not be replaced and will be considered nonresponders.

Sample size may be affected by a pandemic, epidemic, or other emergency not related to the study as described in [Appendix 3](#).

10.4 Interim Analyses

No interim analyses are planned.

10.5 Analysis of Efficacy

10.5.1 Primary Efficacy Analyses

The primary objective assesses the efficacy of AR101 treatment in peanut-allergic subjects aged 1 to < 4 years.

The primary efficacy endpoints are defined by major health authority region.

- **North America:** The primary efficacy endpoint is the proportion of subjects treated with AR101 compared with placebo who tolerate an at least 600 mg single dose of peanut protein with no more than mild allergy symptoms during the exit DBPCFC.
- **Europe:** The primary efficacy endpoint is the proportion of subjects treated with AR101 compared with placebo who tolerate an at least 1000 mg single dose of peanut protein with no more than mild allergy symptoms during the exit DBPCFC.

The ITT population and Farrington-Manning test will be used for these analyses. Subjects tolerating a single dose of at least 600 mg peanut protein for North America and at least 1000 mg peanut protein for Europe will be considered responders; subjects who do not tolerate a single dose of at least 600 mg peanut protein for North America and at least 1000 mg peanut protein for Europe will be considered nonresponders. Nonresponders will also include subjects who withdraw consent or discontinue early anytime before the exit DBPCFC.

Desensitization response rates and associated 95% CIs will be presented for each treatment group using exact Clopper-Pearson CIs. The 95% CI for the treatment difference (desensitization rate for AR101 treatment minus desensitization rate for placebo) will be based on the Farrington-Manning method. The primary efficacy endpoint for North America will be considered met if the lower bound of the 95% CI is greater than the prespecified margin of 0.15. The primary efficacy endpoint for Europe will be considered met if the lower bound of the 95% CI is greater than 0.

